Aim 1A: On the day of surgery, patients will be asked about paresthesia and loss of sensation around the umbilicus. We will document the time when normal sensation returns following the administration of the block. The time elapsed (in minutes) between rectus sheath blockade and the point at which normal sensation returns will be compared between the groups.

Aim 1B: Every 2 hours, we will question the patients regarding their need for pain medication and obtain their Numeric Rating Scale (NRS) pain scores for umbilicus incisional pain. We will document when the patient needs pain medication. The time elapsed (in minutes) from the rectus sheath blockade until the first request for umbilicus pain medication, as well as NRS pain scores will be compared between groups.

Hypothesis:

We hypothesize that rectus sheath injections with the ropivacaine/clonidine combination will be superior in providing long lasting analgesia compared to ropivacaine alone, increasing the duration of sensory block and analgesia, and lowering pain scores at the umbilicus incision.

Aim 2. We will determine if any improvements we observe in pain control satisfaction with the ropivacaine/clonidine combination can be attributed to clonidine's ability to reduce anxiety.

Aim 2A will compare between the two groups patient, parent, and nurse NRS satisfaction scores and correlate them with post-op scores on the state-anxiety component of the State-Trait Anxiety Inventory for Children (STAIC S – Anxiety). Aim 2B will compare postoperative

STAIC S – Anxiety scores between the two groups. Aim 2C will compare within the two groups the difference between the pre and post- op STAIC S Anxiety scores to show if ropivacaine/clonidine is more effective at reducing anxiety.

The methodology will be the following:

Aim 2A: NRS pain control satisfaction scores from patient, parent and nurse will be collected at the completion of the study. State-Trait Anxiety Inventory for Children (STAIC S – Anxiety) questionnaires will be administered to both groups before surgery, and at hour 6 after rectus sheath injections. Post-op anxiety scores in each group will be correlated with satisfaction scores. Aim 2B: The postoperative STAIC S – Anxiety scores will be compared between the 2 groups. Aim 2C: The pre-op STAIC S Anxiety scores will be compared with post- op STAIC S Anxiety within each group.

Hypothesis:

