Inclusion criteria will consist of 1) age 10-17 years, 2) scheduled for elective laparoscopic appendectomy, 3) weight $>/=34\text{kg}$, 4) complete postoperative questionnaires. Exclusion criteria will be 1) patients younger than 10 years and 18 years or older, 2) weight $< 34\text{ kg}$, 3) weight $>/=100\text{ kg}$, 4) patient and family refusal, 5) non-English-speaking patients and families, 6) cognitive impairment, 7) developmental delay, 8) allergies to medications used in the study (hydromorphone, oxycodone, acetaminophen, ketorolac, ropivacaine, and clonidine), 9) need for opioids via a patient controlled analgesia device, 10) patients with a positive pregnancy test, and 11) local infection at planned injection sites

The following patients will be excluded from the study: 1) patients with failed rectus sheath blocks, 2) patients that require opioids via a patient controlled analgesia device, 3) patients with laparoscopic procedure converted to open, 4) patients that will not be able to place the time of return to normal sensation within 1 hour of its occurrence (e.g. sleeping), and 5) patients with no follow-up possible. The patients that will be discharged home before the resolution of paresthesia will be excluded from analysis of the first aim.

Randomization:

The operating room pharmacy will perform the randomization using a computer-generated random number table. The study medications will be labeled as study drug and released in identical syringes with a volume of 11 ml each. Two syringes will be released per patient. Each syringe for Ropivacaine Group (total 2) will contain 10 ml of ropivacaine 0.5% and 1ml of normal saline. Each syringe for the Ropivacaine/ Clonidine Group (total 2) will contain 10 ml of ropivacaine 0.5 %, 1 mcg/kg (0.01 ml/kg) of clonidine (100 mcg =1 ml) and normal saline for a total volume of 11 ml. Patients and all members of the care team, except the pharmacist, will be blinded to group allocation.

Intraoperative Study Protocol:

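### Children whose return of sensation cannot be timed to within 1 hour leave the whole study, although only Aim 1A uses that time; Aims 1B and 2 lose valid data.

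*Combined protocol and SAP*

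**What the plan says.** Section D, Patient eligibility, has a list of five post-enrolment exclusions that opens "The following patients will be excluded from the study". Its fourth item is "patients that will not be able to place the time of return to normal sensation within 1 hour of its occurrence (e.g. sleeping"). The sentence after the list handles a related case differently: "The patients that will be discharged home before the resolution of paresthesia will be excluded from analysis of the first aim".

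Section B defines the outcomes:
- **Aim 1A:** "The time elapsed (in minutes) between rectus sheath blockade and the point at which normal sensation returns".
- **Aim 1B:** "The time elapsed (in minutes) from the rectus sheath blockade until the first request for umbilicus pain medication, as well as NRS pain scores".
- **Aim 2:** the STAIC state-anxiety "questionnaires will be administered to both groups before surgery, and at hour 6 after rectus sheath injections", plus patient, parent and nurse satisfaction scores taken when the child completes the study.

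Section E names no analysis population and does not bring children excluded under item 4 back into any aim. Its sample-size paragraph lists failure to establish when the numbness ends as one of four expected causes of loss.

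**The concern.** The minute at which sensation returns is the outcome of Aim 1A and an input to nothing else. A child who slept through it can still have a time to first request, NRS pain scores, two STAIC scores and three satisfaction scores. As written, all of these are discarded.

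The plan is also inconsistent. A child with no end time because of discharge stays in Aim 2, while a child with an imprecise end time because of sleep leaves it. Neither fact bears on the Aim 2 outcomes.

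The exclusion is decided after randomisation and after the block. At stake are precision in Aims 1B and 2 and, possibly, the comparability of the arms there. Bias in the duration comparison itself is a separate matter and is not argued here.

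**Working it through.** **1. Which outcomes need the time of sensory return**

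| Outcome | Uses that time? | Item 4 child | Child discharged while numb |
|---|---|---|---|
| Aim 1A, time to normal sensation | Yes | Out | Out |
| Aim 1B, first request and NRS pain | No | Out | Out |
| Aim 2, STAIC before surgery and at hour 6 | No | Out | In |
| Aim 2, satisfaction | No | Out | In |

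The two right-hand columns differ only for Aim 2. In the Aim 1B row, both rules remove children whose data do not depend on the time.

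**2. Is the STAIC usually due before the excluding event?** Section E assumes durations of 720 min (SD 288) and 1080 min (SD 432), that is 12 h (SD 4.8) and 18 h (SD 7.2). Assuming normality:
- Ropivacaine: P(T > 6 h) = Φ((12 − 6)/4.8) = Φ(1.25) = 0.894.
- Combination: P(T > 6 h) = Φ((18 − 6)/7.2) = Φ(1.67) = 0.952.

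So in about 89% and 95% of children the hour-6 STAIC falls due before sensation returns.

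**3. Precision.** First the plan's own figures, with a two-sided t-test at 0.05 and 80% power. With SD 288 in both arms and a difference of 360 min, the standardised difference is 360/288 = 1.25, which needs 11.1, so 12 per group, as stated. At 50 per group the detectable standardised difference is 0.566. Multiplied by 288/720 = 0.40 this is 22.6%, which agrees with the stated 23%.

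The same calculation applies to any continuous Aim 2 score, in SD units. The normal approximation is (1.960 + 0.842) × √(2/n).

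| Per arm (assumed) | Normal approximation | t-test |
|---|---|---|
| 50 | 0.56 SD | 0.57 SD |
| 30 | 0.72 SD | 0.74 SD |
| 25 | 0.79 SD | 0.81 SD |

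The documents do not give the number lost to item 4 alone. The 30 and 25 rows are assumptions, not predictions.

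**4. Can the direction of any differential loss be settled?** The documents give no block times or sleep hours. Assume sleep from 22:00 to 07:00 and durations as above, either normal or lognormal with the same means and SDs. The share of children whose sensation returns during those hours is then:

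| Block time (assumed) | Model | Ropivacaine | Combination |
|---|---|---|---|
| 10:00 | Normal | 47% | 47% |
| 10:00 | Lognormal | about 37% | 55% |
| 16:00 | Normal | 63% | 34% |

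The gap vanishes, reverses or is large depending on inputs that the plan does not supply. These are also not exclusion rates: two-hourly questioning may let some children place the time.

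**The case against.** **It was meant for Aim 1A only.** Possibly. But the list says the study, and the next sentence shows that the plan confines an exclusion to one aim when it intends to. An analyst following the text would drop these children everywhere.

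**The other outcomes are tied to resolution.** In part this stands. Two-hourly assessment stops at resolution or discharge. Satisfaction is taken at study completion, and the Study Duration paragraph ends the study once block resolution has been assessed. Only the hour-6 STAIC is at a fixed time. Still, the assessment that finds the numbness gone closes follow-up whether or not the exact time is known.

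**The loss allowance brings Aim 2 down to 12 per arm.** A reader might infer this from the step from 12 to 50 per group, which corresponds to a loss of 1 − 12/50 = 76%. The documents do not support it. The allowance was set for block duration and covers four causes. One of them is discharge, which does not remove a child from Aim 2. Dropouts and unsuccessful blocks would remain losses whatever is done about item 4.

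**Sleeping children are less anxious, so Aim 2 is biased.** This too is tempting. Section C lists sedation among the reported effects of clonidine, and exclusion depends on sleep and on block duration, which treatment is expected to change. But sleep when sensation returns, at planned means of 12 and 18 hours, is not the same as sedation or anxiety at hour 6. The night-time shares model only clock time and duration, not anxiety or satisfaction. Bias is possible; it is not shown.

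**This is a pilot and Aim 2 is secondary.** True, and no power is claimed for Aim 2. That limits the weight of the point, but the correction is only a few sentences.

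**Conclusion.** The concern holds as a defect of scope. Item 4 removes randomised, treated children from Aims 1B and 2 for want of a time that those aims do not use, and it conflicts with the discharge rule for Aim 2. The supported harm is avoidable loss of valid data.

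The size depends on an unstated share. Over an assumed range of 50 down to 25 per arm, the detectable difference rises from 0.57 to 0.81 SD (two-sided 0.05, 80% power, equal arms). The 89% and 95% figures rest on the plan's means and SDs and on normality. The size and direction of any bias in Aim 2 cannot be determined from the documents. The point should be corrected; it does not undermine the primary aim.

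**What to change.** In Section D, Patient eligibility:
1. Take item 4 out of the whole-study list and limit it to the Aim 1A analysis of time to normal sensation.
2. State that these children stay in Aim 1B and Aims 2A to 2C with all data collected.
3. State that satisfaction scores are still collected when the time of resolution is imprecise.
4. State that an untimed resolution does not by itself fail the fourth inclusion criterion, which asks for complete questionnaires after surgery. Otherwise that criterion could exclude the same children again.
5. Limit the discharge exclusion to Aim 1A as well, or say why discharged children leave Aim 1B. Without this, untimed children would stay in Aim 1B while discharged children do not.

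The cost is a few sentences, with no new visits or measures. The Aim 1A sample is unchanged by item 1. The downside is a different denominator for each aim, which the plan already accepts for discharged children; each table should report its own.

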In the operating room, standard anesthesia monitors will be connected and general anesthesia will be performed as per the anesthesiologist's standard of care. At the completion of surgery, acetaminophen iv and ketorolac will be administered by the anesthesia provider. Dexmedetomidine will not be administered during anesthesia or after the completion of anesthesia. A member of CHP Acute Interventional Perioperative Pain Service (AIPPS) – attending or fellow will perform all bilateral ultrasound guided rectus sheath blocks as per CHP standard of care using the study drug. The surgeon will not infiltrate the local anesthetic at the laparoscopic instrument sites.

Postoperative Study Protocol:

For the following 24 hours, the analgesic regimen will include ketorolac every 6 hours (if not contraindicated by surgeon), acetaminophen iv every 6 hours, oxycodone by mouth as needed for pain, every 4 hours, and hydromorphone iv as needed for pain, every 2 hour.

In the postoperative period the patients will be asked to complete a few questionnaires created for this study. The nurse taking care of the patient, principal investigator, one of the co-investigators, or the research assistant will do the assessment. Starting in the PACU, the patients will be questioned about the presence of paresthesia around the umbilicus instrument site ("is the area around your belly button numb") and the umbilical pain severity using NRS scale (0 being no pain and 10 the worst imaginable pain). They will also be asked about their need for pain medication for umbilical pain as well as the amount of pain medication they have consumed for pain in that region. The assessment will continue on the floor every 2 hours until complete resolution of paresthesia at the umbilicus or until the patient is discharged home. The state version (S-anxiety) of the State-Trait Anxiety Inventory for Children (STAIC) will be administered to measure patient anxiety before surgery after the consent is done and 6 hours after rectus sheath injections. At the completion of the study,

the patient's, parent's, and nurse's satisfaction with pain control will be investigated using an NRS scale (0 being very unsatisfied and 10 being very satisfied).

E. STATISTICS: ASSESSMENT OF ADEQUACY OF SAMPLE SIZE

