Descriptive statistics will be presented as frequencies (percentages, %) for categorical data or as mean \pm standard deviation (SD) or median and interquartile range for normally or non-normally distributed continuous data, as appropriate. Examination of normal distribution assumption for continuous data will be determined by q-q plots and histograms. Two sample T-Test or Wilcoxon-Mann-Whitney test will be performed to determine differences between groups for normally or non-normally distributed continuous data, respectively. Pearson's chi-square or Fisher's exact test, as appropriate, will be used to compare the frequency distribution of categorical variables between the groups. We will compute Pearson correlation coefficient between NRS pain scores and the anxiety scores. If the assumptions for the parametric test are not met, a nonparametric alternative will be used (i.e. Spearman correlation coefficient).

Sample Size and Power:

The target sample size was calculated with the assumption that the duration of block in the group with ropivacaine only is 720 minutes \pm 288 minutes and in the group with ropivacaine and clonidine the duration is 1080 minutes \pm 432 minutes. The difference would be clinically relevant if the duration of blocks with ropivacaine and clonidine will be at least 50% or more than the duration of blocks with local anesthetic only. Assuming a power of 80%, a level of significance of 0.05, mean and SD as above, only 12 patients would be required in each group. Allowing for a 400% loss arising from patient dropout, unsuccessful block, incomplete follow up because of discharge home on the day of surgery, and inability to determine when paresthesia wears off, we plan to recruit 50 patients in each group, for a total of 100 patients. We estimate that this sample size of 100 patients would provide 80% power to detect a difference as small as 23% in the duration of paresthesia between these 2 groups.

F. SIGNIFICANCE AND APPLICABILITY

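### Aim 1 drops every patient discharged while still numb, which removes the longest block durations and would understate a true clonidine effect if discharge timing is similar in both arms

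*Combined protocol and SAP*

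**What the plan says.** Section D, Patient eligibility, has three layers of selection.

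- **Aim 1 only:** "The patients that will be discharged home before the resolution of paresthesia will be excluded from analysis of the first aim". Section B defines aim 1 as both 1A (return of sensation) and 1B (time to first request for umbilical pain medication, and pain scores).
- **Whole study:** the list of removals includes "patients with failed rectus sheath blocks, 2) patients that require opioids via a patient controlled analgesia device", conversion to open surgery, "patients that will not be able to place the time of return to normal sensation within 1 hour of its occurrence", and no possible follow-up.
- **Entry:** the inclusion criteria contain "4) complete postoperative questionnaires", which cannot be known at entry.

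The pharmacy randomises and releases coded syringes, and the pain service performs the "rectus sheath blocks as per CHP standard of care using the study drug". A failed block and the later events therefore come after allocation. Blinding is planned: "Patients and all members of the care team, except the pharmacist, will be blinded to group allocation".

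On follow-up, the Postoperative Study Protocol says "The assessment will continue on the floor every 2 hours", ending when numbness has resolved or the patient goes home. Section E plans a t-test or Wilcoxon test for continuous outcomes. It covers the losses by recruiting more: "Allowing for a 400% loss arising from patient dropout, unsuccessful block", together with same-day discharge and untimed return. The documents describe no censored analysis, no all-randomised or all-treated set, and no sensitivity analysis for removed patients.

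**The concern.** A patient discharged while numb is dropped because the block outlasted the stay. The rule therefore deletes long durations, and it deletes more of them in whichever arm lasts longer. That happens even when both arms have the same discharge times and blinding holds. Extra recruitment restores numbers but leaves the selection in place.

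At stake is the quantity the trial is built to estimate. Section E treats a gain of at least 50% as clinically relevant. A true gain of that size could be reported well below the threshold and dismissed. Section F says the hospital wants earlier discharge, which would enlarge the loss. The rule also throws away first-request times and pain scores already recorded before discharge.

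The other removals can depend on outcome or arm as well. The Background lists sedation as a clonidine effect, and sleeping is the protocol's own example of why a return of sensation may go untimed.

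**Working it through.** **The plan's own figures.** Section E assumes 720 min (SD 288) for ropivacaine and 1080 min (SD 432) for the combination. The difference is 1080 - 720 = 360 min and the ratio 1080/720 = 1.50. The stated 12 per group reproduces with SD 288 in both arms: 2 x (1.96 + 0.842)^2 x 288^2 / 360^2 = 10.05, so 11 by the normal formula and 12 by the t-based one. Using both stated SDs gives 18. That is a separate matter; both stated SDs are used below.

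**Model (assumed).** Durations are gamma with shape (mean/SD)^2 = (720/288)^2 = (1080/432)^2 = 6.25. Discharge time from the block has the same distribution in both arms. A patient is analysed only if the duration does not exceed the discharge time.

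**Closed form for discharge at 1440 min (24 h).** Retained fraction = F(6.25); retained mean = mean x F(7.25)/F(6.25). F(k) is the gamma distribution function with shape k at 1440/scale; scale = mean/6.25, i.e. 115.2 and 172.8 min.

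- Ropivacaine: retained 0.981; mean 720 x 0.958/0.981 = 703 min.
- Combination: retained 0.812; mean 1080 x 0.694/0.812 = 923 min.
- Difference 923 - 703 = 220 min; ratio 1.31.

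**Other assumed patterns** (uniform over the range, 2 million draws per arm):

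| Discharge after block | Removed, ropivacaine vs combination | Analysed means (min) | Difference (min) | Ratio |
|---|---|---|---|---|
| nobody removed | 0% vs 0% | 720 vs 1080 | 360 | 1.50 |
| 24-36 h | 0.5% vs 8% | about 715 vs 1005 | 290 | about 1.4 |
| all at 24 h | 2% vs 19% | 703 vs 923 | 220 | 1.31 |
| 10-30 h | 15% vs 40% | 659 vs 867 | 208 | 1.32 |
| 8-24 h | 27% vs 57% | 620 vs 777 | 157 | 1.25 |

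Lognormal or normal durations give 116 to 306 min over the same four discharge patterns, always below 360.

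**No true effect.** With equal durations and equal discharge timing, the planned test rejected in about 4 to 6% of simulated trials, close to nominal.

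**Failed blocks.** Score failures as zero, at assumed rates:

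- 10% in each arm: 0.9 x 1080 - 0.9 x 720 = 972 - 648 = 324 min, ratio still 1.50.
- 10% in ropivacaine only: 1080 - 648 = 432 min.
- 10% in the combination only: 972 - 720 = 252 min.

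The direction depends entirely on rates the documents do not give.

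**Power, 50 per arm** (simulated; 10% failures in each arm assumed). Log-rank in all block recipients, failures counted as shortest, against the planned t-test in the restricted set:

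- 10-30 h: about 0.97 vs 0.87
- 8-24 h: about 0.95 vs 0.63
- 24 h: about 0.98 vs 0.92
- 24-36 h: about 0.99 vs 0.99

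With 10% vs 30% failures and discharge at 24 h, the order reverses: 0.74 vs 0.89. Log-rank among working blocks only, with discharge censored, keeps about 0.95 or more throughout.

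**The case against.** The best defence has four parts.

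- **Length of stay.** Section F says uncomplicated cases stay at least one day. At 24 h or later the planned t-test still has power of about 0.92 to 0.99, so a reader who infers that the trial is underpowered because of this rule goes too far. That stands. The understatement does not disappear, though: the ratio is still 1.31 to about 1.4. Section E itself allows for same-day discharge.
- **Direction.** The rule might be read as always shrinking the difference. The documents do not support that, because it requires a true clonidine effect and similar discharge timing. The Preliminary studies text says pain can delay discharge, and the Background lists sedation, so timing could differ by arm in either direction.
- **Estimand.** Whether clonidine prolongs a working block is a fair question for a blinded pilot. Blinding makes deliberate unequal removal unlikely, though it cannot prevent imbalance caused by the drug. A reader might infer that dropping failed blocks and PCA patients favours clonidine; nothing in the documents shows this. Section G notes that analgesics may be needed for pain elsewhere, so PCA use is not in itself block failure.
- **The 18-24 h figure.** It is tempting to take the Study duration entry as the discharge time. It runs from consent to the end of block-resolution assessment, so it cannot be used that way.

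The questionnaire criterion may be loose drafting for willingness to complete the forms. It is a minor part of this point.

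**Conclusion.** The point holds for the discharge rule, with a conditional direction. If clonidine prolongs the block and discharge timing is similar in both arms, excluding patients who go home numb understates the gain. Under the plan's means and SDs, gamma durations and the four assumed discharge patterns, a true 360 min is observed as 157 to 290 min. The ratio falls from 1.50 to between 1.25 and about 1.4. The exact size is unknown because the documents give no discharge times. The rule is conservative: under equal discharge timing it does not manufacture an effect.

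The removals for failed block, PCA and untimed return are post-randomisation and potentially related to outcome or arm. The documents support no direction or size for them. They call for transparent reporting and a second analysis, and do not justify a claim that the comparison is invalid. The change should be made; confidence in the size is moderate.

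**What to change.** 1. **Discharge rule.** Delete the exclusion. For aim 1A, right-censor at the last assessment when the patient was numb. For aim 1B, keep any recorded first request; if there was none, censor at the last assessment before discharge. Compare arms by Kaplan-Meier and log-rank.
2. **Untimed return.** Keep these patients. Use the interval between the last numb and first non-numb assessments with an interval-censored method, such as an interval-censored log-rank test or a parametric survival model. An ordinary log-rank test cannot use intervals, so midpoint imputation should serve only as a sensitivity analysis.
3. **Other removals.** Report all of them by arm and reason. Beside the working-block analysis, present one of all randomised patients who received the block, by assigned arm. Define failed block in advance, judge it blind and count it as the shortest duration. State a rule for handling conversions to open surgery in the analysis. Analyse PCA patients both censored at PCA start and counted as events, since censoring there may be informative.
4. **Questionnaires.** Treat missing forms as missing data and drop completion as an entry criterion.

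The cost is protocol and SAP wording, plus continued recording of the same ward assessments in patients who would have been removed. There are two downsides. The log-rank test assumes discharge time is unrelated to remaining numbness. The all-recipients analysis is diluted by technical failures and loses power if failures differ by arm, which is why it should stand beside the censored working-block analysis.

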Selecting the ideal nerve block for laparoscopic appendectomies is a difficult task; nerve blocks traditionally contain only local anesthetic, and it is challenging to find a local anesthetic that not only possesses minimal side effects, but also outlasts pain, relieves anxiety and improves satisfaction with pain control. For instance, even though single injection ultrasound guided rectus sheath blocks provide satisfactory postoperative analgesia after pediatric laparoscopic appendectomy, they tend to be short-lived. To overcome the limitations inherent to local anesthetics, adjuvant medications have been added to nerve blocks, with the hope that the resulting combination will provide patients with better pain control. Clonidine—an alpha 2 adrenoreceptor agonist—is one such medication, and a few small pediatric studies have shown a weak trend in favor of clonidine prolonging analgesia for some blocks, without examining its anxiolytic properties. Our preliminary experience supports the notion the clonidine may assist with pain control, as we have found that a ropivacaine/ clonidine rectus sheath blockade increases the duration of sensory blockade and analgesia. The goal of this pilot study is to build upon these observations and examine whether ropivacaine/ clonidine is effective at prolonging analgesia beyond the effects of ropivacaine alone for laparoscopic appendectomies. Additionally, we plan to investigate the underlying mechanism (i.e. anxiety reduction) that may make this combination better suited for postoperative pain control. Ultimately, results from our study will help us devise better therapeutic regimens for our patients.

One hundred pediatric patients (10-17 years old) scheduled for laparoscopic appendectomy will be randomized into one of two treatment groups—the Ropivacaine Group or the Ropivacaine/Clonidine group—after which they will receive bilateral injections of the corresponding blocking agents in the posterior rectus sheath, at the umbilicus location. Patients in the Ropivacaine Group will receive ropivacaine 0.5% (20 ml), while patients in the Ropivacaine/ Clonidine Group, will receive ropivacaine 0.5% (20 ml) and clonidine (2mcg/kg).

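### Weight sets the ropivacaine mg/kg in both arms and the clonidine amount in one, yet the Aim 1A duration comparison does not use it: a valid test that may give up precision and cannot show whether the effect changes with weight

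*Combined protocol and SAP*

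**What the plan says.** - **Dosing.** The opening summary gives the control regimen: "Patients in the Ropivacaine Group will receive ropivacaine 0.5% (20 ml" ml in total. The combination arm "will receive ropivacaine 0.5% (20 ml) and clonidine (2mcg/kg" in total. Section D, Randomization, describes the preparation: "Two syringes will be released per patient", each made up to 11 ml. In the combination arm each syringe "will contain 10 ml of ropivacaine 0.5 %, 1 mcg/kg (0.01 ml/kg) of clonidine".
- **Weight range.** Section D, Patient eligibility, admits patients from 34 kg and excludes those at 100 kg or more.
- **Allocation.** A computer-generated random number table is used. No stratification is described.
- **Endpoint and test.** For Aim 1A (Section B), the time "between rectus sheath blockade and the point at which normal sensation returns will be compared between the groups". Section E gives the method for continuous data: "Two sample T-Test or Wilcoxon-Mann-Whitney test will be performed to determine differences between groups", with the choice depending on normality.
- **Not described.** No weight covariate, weight subgroup or display of the effect by weight appears anywhere.

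**The concern.** The dosing rule builds weight into the treatment. One drug is fixed in mg and the other per kg, so their ratio changes across the enrolled patients. If weight is related to how long the block lasts, an unadjusted comparison leaves that variation in the error term.

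The plan would also report a single average effect for a combination whose clonidine content differs about 3-fold between the lightest and heaviest patients. Section C quotes clonidine both in total mcg (30-300 in the adult meta-analyses) and per kg (1-2 mcg/kg), so it does not settle which scale governs the effect. The trial could at least describe this, but no such output is planned.

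Weight is already held for every patient, because it is an eligibility criterion and is needed to fill the syringes. If it is added only after an imbalance has been seen, the adjustment is post hoc.

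**Working it through.** **1. Dose check against the plan.** Two syringes x 1 mcg/kg = 2 mcg/kg, and 2 x 10 ml = 20 ml. Both agree with the opening summary. Ropivacaine 0.5% is 5 mg/ml, so 20 ml x 5 = 100 mg at any weight.

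**2. Range over eligible weights.**

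| Quantity | Formula (w = weight in kg) | 34 kg | Just under 100 kg |
|---|---|---|---|
| Ropivacaine, mg | 100 | 100 | 100 |
| Ropivacaine, mg/kg | 100/w | 2.94 | about 1.0 |
| Clonidine, mcg/kg | 2 | 2 | 2 |
| Clonidine, total mcg | 2w | 68 | just under 200 |
| Clonidine in syringe, mcg/ml | w/11 | 3.1 | 9.1 |
| Clonidine to ropivacaine, mcg/mg | 2w/100 | 0.68 | 2.0 |

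Each varying row changes by a factor of 100/34 = 2.94.

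**3. Validity of the planned test.** A simulation used 20,000 trials per setting, weights uniform on 34-100 kg, SD 288 min, no treatment effect, a common weight slope and no exclusions. For weight-duration correlations of 0, 0.3 and 0.5, at 12 and at 50 per arm, type I error was 0.047 to 0.051 and mean bias was within 1.5 min of zero.

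**4. What adjustment gains and costs.** Let r be the within-arm correlation of weight with duration. It is not in the documents, so 0 to 0.5 is assumed. Adjustment multiplies the variance of the treatment difference by (1 - r^2). Estimating the slope multiplies it by about 1 + 1/(2n - 4) with n per arm: 1 + 1/20 = 1.05 at n = 12, and 1 + 1/96 = 1.010 at n = 50.

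| r | 1 - r^2 | Net factor, n = 12 | Net factor, n = 50 |
|---|---|---|---|
| 0 | 1.00 | 1.05 | 1.01 |
| 0.1 | 0.99 | 1.04 | 1.00 |
| 0.2 | 0.96 | 1.01 | 0.97 |
| 0.3 | 0.91 | 0.96 | 0.92 |
| 0.5 | 0.75 | 0.79 | 0.76 |

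Break-even is where (1 - r^2) x (1 + 1/(2n - 4)) = 1. This gives r = sqrt(1/21) = 0.22 at n = 12 and r = sqrt(1/97) = 0.10 at n = 50.

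In terms of detectable difference at 50 per arm, take 80% power, two-sided 0.05 and a coefficient of variation of 40% in both arms (288/720 = 432/1080 = 0.40). The figure is 25.7% at r = 0, 24.4% at 0.3 and 21.8% at 0.5, before the 1% cost.

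**5. Chance imbalance.** The standardised weight difference between arms has SD sqrt(2/n): 0.41 at n = 12 and 0.20 at n = 50. The probability that it exceeds 0.5 SD is 22% and 1.2% respectively. With the root-mean-square planning SD, sqrt((288^2 + 432^2)/2) = 367 min, a 0.5 SD imbalance moves the estimate by 0.5 x r x 367. That is 0 at r = 0, 55 min at 0.3 and 92 min at 0.5, against a planned difference of 360 min.

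The 12 and 50 per arm are Section E's calculated requirement and its recruitment target. They serve here only as the two ends of a range.

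**The case against.** The strongest reply is that nothing is wrong with the planned test. Ropivacaine is given identically in both arms, and randomisation balances weight in expectation. The standard error already carries chance imbalance, and the planning SDs are total SDs, so they should already include any spread due to weight. All of this stands. A reader might infer that the comparison is biased, or that a weight imbalance would distort it unchecked. The documents do not support that, and step 3 shows the error rate holding.

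A reader might also infer that both doses vary 3-fold. On any single scale only one does: clonidine in mcg, ropivacaine in mg/kg. The 3.1 to 9.1 mcg/ml is a syringe concentration, and the documents give none at the nerve.

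Third, no passage states that weight or mg/kg affects the duration of numbness. Section C links more anesthetic at one site to longer analgesia, but in mg per site every patient receives the same ropivacaine. The correlation may therefore be near zero, where adjustment gains nothing.

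Fourth, the arms may have different slopes. If duration rose with ropivacaine mg/kg and also with clonidine amount, weight would act downward in the control arm and in both directions in the combination arm. A common weight term would then recover less than step 4 suggests. An interaction estimated from few patients would be imprecise.

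The last two points limit the gain. They do not remove the case for a covariate whose cost is small and whose value cannot be judged in advance, nor for an exploratory look at effect by weight.

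**Conclusion.** The point holds as a matter of precision and description, not validity. The dosing rule makes the clonidine amount and the clonidine-to-ropivacaine ratio rise 2.94-fold with weight in the combination arm, and ropivacaine mg/kg fall by the same factor in both arms. The analysis makes no use of a variable the trial already holds.

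The size is uncertain because r is unknown. Over the assumed 0 to 0.5, the net effect of adjusting runs from a 5% rise in variance to a 21% fall at 12 evaluable per arm, and from a 1% rise to a 24% fall at 50. These figures assume a common slope.

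Twelve evaluable per arm should not be read as a forecast. Section E presents it as the number required and recruits 50 per arm to cover losses, so the 22% imbalance risk is the unfavourable end. Exclusions after randomisation, including discharge before numbness resolves, could disturb weight balance among those analysed. A weight term would address measured imbalance in weight, but not that selection. This is a recommended improvement to the plan, not the correction of an error.

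**What to change.** In Section E, prespecify the Aim 1A block-duration comparison as a linear model with treatment and baseline weight (continuous), reporting the weight-adjusted difference with its confidence interval. State in advance what applies if durations are non-normal: the same model on log duration, or a rank-based ANCOVA. Keep the planned t-test or Wilcoxon-Mann-Whitney test as a sensitivity analysis. Show the weight-by-treatment interaction, for example as the estimated effect across the weight range, labelled exploratory.

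Dosing and syringe preparation are outside this point and stay as they are. Clonidine mcg (2 x weight) and ropivacaine mg/kg (100/weight) both follow from weight, so they need no separate recording.

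The cost is a few sentences in Section E, one degree of freedom, and a small loss of precision if weight turns out not to be prognostic (about 5% in variance at 12 per arm, about 1% at 50). The wording should be settled before unblinding.
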